#### 9.2.1 Dose and administration

The product for the skin test is administered as per the prescribing information for RTA by healthcare professionals who have a certificate to perform the RTA test, appropriate training, and experience with the test. Blood samples will be collected by a staff member who is authorized, trained, and experienced in blood collection for the T-SPOT.TB assay.

The number assigned to the study subject should match the subject identification number on the package of the investigational medicinal product.

*Administration of the product for the skin RTA test:*

- The investigational medicinal product should be removed from the refrigerator half an hour before administration.
- The expiry date should be checked before administration.

- The investigational medicinal product may be administered only if it has the appearance of a clear and colorless solution.
- Injection site disinfection is not required before administration. If the injection site does get disinfected, it must be allowed to dry completely before administration of the investigational medicinal product.
- At Visit 1, the Investigator documents in which forearm the investigational medicinal product should be injected in the CRF.
- As per the RTA prescribing information, a dose of 0.1 mL should be administered using a 1.0-mL sterile disposable syringe with a 26-gauge short-bevel needle.
- The skin is slightly stretched, and the needle is held almost parallel to the skin, with the bevel facing upward. The needle should be inserted about 2 mm deep into the inner surface on the mid-third of the left or right forearm. The needle should be visible through the epidermis, and 0.1 mL of the investigational medicinal product is slowly injected intradermally. When placed correctly, the injection should produce a small papule on the skin, 8 to 10 mm in diameter. The papule will resolve in about 10 minutes.

The absence of a papule at the time of the intradermal RTA injection (as described above) should be documented in the CRF, providing a reason. Repeated administration of RTA to the same volunteer is not allowed. The volunteer should come to the follow-up visits as part of the study for safety monitoring. Volunteers without a papule after the intradermal injection of RTA are excluded from the analysis.

After injection, the syringe and needle should be disposed of as a unit in a labeled puncture-resistant container.

### **9.2.2 Packaging and labeling**

The T-SPOT.TB assay and the RTA test are used routinely in specialized facilities, with all packaging requirements in place.

### **9.2.3 Transportation of the investigational medicinal products**

The T-SPOT.TB assay and the RTA test are used routinely in specialized facilities. Transportation of the investigational medicinal product is not applicable in this study.

### **9.2.4 Storage conditions**

The shelf life of RTA is 24 months when stored in a refrigerator at +2 °C to +8 °C, which will be monitored during the study.

Vials should be stored in cartons until the administration of the product. The expiry date is printed on the outer label of the carton.

At each study site, the investigational medicinal product should be stored in a refrigerator with a temperature control system and an alarm system.

In case of malfunction of the refrigerator storing the investigational medicinal product, it should be placed in another refrigerator as soon as possible. The reason and time when the investigational medicinal product was transferred to another place should be documented in a temperature control log.

The product must not be used if the Principal Investigator has found significant deviations from the recommended storage conditions. The Principal Investigator should discuss with the Clinical Study Leader whether the product should be disposed of or can be used in the study.

Monitoring of storage conditions shall be the responsibility of the study staff.

#### **9.2.5 Procedure for generating a study participant number**

On the day of screening, volunteers arriving at the center will be numbered consecutively (the first participant arriving will receive the lowest screening number). The individual volunteer number will be recorded in the informed consent and will be recorded in the individual sign-in cards at the visits thereafter.

The screening number is the individual volunteer number.

##### **Method of generating a study participant number:**

Each volunteer will be assigned the lowest available number during visit 0.

The available numbers in the study sites will be generated as follows:

The first digit is the first letter of the city where the study site is located;

The second to fourth digits are the smallest available three-digit number starting from 001.

#### **9.2.6 Blinding & unblinding of data**

This is an open-label study, and, hence, the study staff and subjects will be aware of the study stage and the products being administered. Subjects' data will only be present in informed consent forms which will not be shared or processed during the study, including all visits. Only study subject numbers will be available when the data are processed.

#### **9.2.7 Compliance with the administration regimen of RTA and T-SPOT.TB**

All procedures will be performed by the study staff during visits in a controlled environment. Monitoring of compliance with the administration regimen is not applicable in this clinical study.

#### **9.2.8 Accounting for the investigational medicinal products**

The T-SPOT.TB assay and the RTA test are used in routine practice. Product accounting beyond that is available at a given study site is not applicable.

#### **9.2.9 Precautions and overdosage**

As per the RTA prescribing information, transient signs of a general reaction, such as malaise, headache, and pyrexia, may rarely occur. These reactions, if any, will be documented in the CRF. No anaphylactic reactions associated with the tuberculin test have been observed. However, the necessary means to manage an anaphylactic reaction should always be available at the study site. The skin tests will be performed as per the current Russian guidelines for the diagnosis of tuberculosis which stipulate that these tests should be performed annually in certain subpopulations.

Venous blood draws may be associated with a minimal risk which could not jeopardize life or health.

### 9.2.10 Concomitant medication therapy

During the study, information on concomitant medication therapy considered relevant for the subject should be recorded on the appropriate pages of his/her CRF.

A decision to withdraw a subject from the study will be at the discretion of the Responsible Investigator. Drugs and live vaccines listed in Section 8.6 are among the non-inclusion criteria.

### 9.3 Study activities

Visit number	0	1	2	3
Study days	Day -3 to 0	0	3	28
Informed consent procedure - assignment of a study participant number	×			
Collection of the information relevant to the inclusion/non-inclusion criteria	×			
Medical history, symptoms	×	×	×	×
Medical examination	×	×	×	
Blood sampling for the T-SPOT.TB assay	×			
The RTA skin test (0.2 µg)		×		
Documentation of AEs		×	×	×
Reading of the RTA intradermal test result			×	

-  A Screening Visit (Visit 0) is performed within 3 days before an Enrollment Visit (Visit 1)
-  A Final Visit is performed if the subject discontinues the study before Visit 3 (Day 28).
-  The medical examination which includes a review of complaints and assessment of clinical symptoms is performed per the current guidelines. The examination must include measurements of body weight, height (only at screening), and body temperature, BP, HR, RR (performed according to the regulations adopted in Russia).

#### 9.3.1 Assessment of specificity

Specificity is a key characteristic of a diagnostic assay, referring to its ability to correctly identify individuals without the disease.

The specificity of the RTA test is defined as the proportion of subjects who tested negative (no infiltration (papule) in the injection site) in a healthy population (i.e. without MTb exposure).

$$\text{Specificity} = \frac{\text{True negatives}}{\text{True negatives} + \text{False positives}}$$

#### 9.3.2 Safety assessments

Local and systemic AEs will be evaluated based on observations made during the first hour after the administration of the investigational medicinal product and on health assessments performed

at follow-up visits on Days 3 and 28 after the administration of the investigational medicinal product. Medical examinations will be performed during all visits.

The Investigator will assess all AEs and will also report any serious AEs as described in Section 11.3. Any local or systemic AEs should be documented in the CRF.

All volunteers should be monitored by experienced medical staff at the study site for one hour after the interventions. Immediate-onset AEs, if any, should be documented in the CRF.

The intolerance assessment criteria include the frequency of AEs that occurred during the follow-up period.

Note: values obtained and documented at Visit 0 will be considered baseline.

### **9.3.3 Collection and handling of blood samples**

Blood samples will be collected by venipuncture performed by trained healthcare professionals as per the standard protocols for medical manipulations.

#### **Blood samples for the T-SPOT.TB assay**

The T-SPOT.TB assay is used, stored, and analyzed according to the manufacturer's manual.

Blood is drawn from a vein into heparinized tubes (with a green cap). The first portion of blood should go into the heparinized tube. The volume of blood to be drawn for the study is 8 mL (one 8-mL tube or two 4-mL tubes). Immediately after drawing of the blood sample, the tube should be carefully turned upside down 3–4 times to prevent foaming and without shaking so that the blood is evenly mixed with the anticoagulant. The tubes are transported to the laboratory in the upright position at a temperature between +18 °C and +25 °C in a place protected from direct sunlight. The tubes must not be refrigerated or frozen. Each tube must be labeled with the full name (or the individual number of the subject), date, and time of blood collection. The accompanying form must clearly and legibly state the unabbreviated full name (or the individual number of the subject), date of birth, time and date when the material was collected. Non-compliance to the recommendations for the timeframe and temperature for storage and shipping, errors in the accompanying form and tube labeling may result in erroneous or invalid test results.

The T-SPOT.TB assay will be performed at certified laboratories in the participating regions. Subjects' numbers will be used as identifiers to ensure their confidentiality.

#### **9.3.4 Schedule**

An application to authorize the study is submitted to the local ethics committee (LEC) of the NMRC TPID in Q4 2021.

The date of the first visit of the first volunteer (First Volunteer In) is Q4 2021.

The date of the last visit of the last volunteer (Last Volunteer Out) is Q1 2022.

## 10. ETHICAL ASPECTS

Informed consent should be obtained from each volunteer as per local requirements after he or she has been informed of the nature of this study. Data collection and processing will be performed in compliance with all confidentiality principles.

All study participants will be examined in accordance with normative documentation in force in the Russian Federation. Volunteers will be informed that their consent to participate in the study is voluntary and that they may withdraw it at any time, without stating the reason or being sanctioned.

Approval will be obtained from the LEC of the NMRC TPID before the study commencement.

The total amount of blood to be drawn from each volunteer is approximately 8 mL. Blood samples will be coded before being sent to the laboratory so that only the Principal Investigator and study staff have access to the information linking the laboratory results to the individual volunteer number.

Volunteers should not expect any benefit from participating in the study, except for the benefit of a detailed health assessment to be conducted during the study.

### 10.1 Remuneration of subjects

Volunteers will not be paid for participation in the study.

### 10.2 Independent Safety Data Monitoring Committee

Subjects are expected to be exposed to only minimal risks during the clinical study. The Principal Investigator and Responsible Investigator of the study site shall be responsible for the safety of subjects in daily clinical practice. A single fixed dose of the investigational medicinal product RTA will be administered to each subject during the study. Because the study has the design described above, an independent safety data monitoring committee is not required.

## 11. ADVERSE EVENTS

This section discusses the procedures for documenting and reporting AEs during the study. Relevant definitions and terms are presented. Serious AEs should be immediately reported to the NMRC TPID.

### 11.1 Definitions and terms

An adverse event (AE) is any unfavorable medical event detected in a patient or study participant after intradermal administration of the diagnostic test product and blood sampling, which may not have a causal relationship with its use. Thus, an adverse event (AE) can be any unfavorable symptom (including abnormal laboratory findings), complaint, or disease, the occurrence of which does not exclude a causal relationship with the use of the medicinal (investigational) product, regardless of the causal relationship with the medicinal product [ICH GCP E6(R2)].

**A serious AE (experience) or reaction** is any adverse medical event that is, regardless of the dose:

- \* results in death,
- \* is life-threatening,

NOTE: the term “life-threatening” in the definition of “serious” means an event during which the volunteer was under threat of death; it does not concern an event that could theoretically lead to death, was it more severe.

\* requires hospitalization or prolongation of hospitalization,

\* leads to persistent or significant incapacity/disability or

\* is a congenital abnormality/malformation.

- Adverse events should be recorded in the CRF using medical terminology.
- Adverse events will be reported in accordance with local regulations.

### 11.2 Conventional adverse events reporting

The Investigator shall be responsible for documenting in CRFs all AEs that were reported at each visit. The Investigator should use the following terms:

The causal relationship between an AE and the study tests is assessed using the following terms:

- Unrelated
- Possibly related
- Probably related
- Definitely related

The severity of an AE is assessed using the following terms:

- Mild (i.e. tolerated easily)
- Moderate (i.e. interfering with day-to-day activities)
- Severe (i.e. precluding normal functioning)

The outcome of an AE is assessed using the following terms:

- Death
- Unresolved to date
- Resolved with sequelae
- Resolved without sequelae
- Unknown

Note. If an AE persists at the last visit, the Investigator should monitor it until it resolves or stabilizes.

The seriousness of an AE is assessed based on answers to the following questions:

- Did the event lead to death?
- Was the event life-threatening?
- Did the event require inpatient admission or prolongation of existing hospitalization?
- Did the event result in severe or permanent disability or incapacity?
- Does the event appear to be medically relevant?

To avoid confusion or misunderstanding of the difference between the terms “serious” and “severe,” which are not synonymous, the following explanatory note is provided:

The term “severe” is often used to describe the intensity (severity) of a specific event (e.g. mild, moderate, or severe myocardial infarction). However, the event itself may have relatively little medical significance (e.g., severe headache). The meaning of this definition is different from that of the term “serious,” which is based on patient/event outcomes or action criteria typically associated with events that are life-threatening or jeopardize the functioning of the subject. Seriousness (rather than severity) serves as a benchmark for determining regulatory reporting requirements.

### **11.3 Immediate reporting of serious adverse events by the Investigator**

The Investigator documents a serious AE (see definitions in Section 11.1) in the CRF and is responsible for completing the serious AE reporting form (see a template in Appendix 5).

Any serious clinical AE (including death and overdose) that occurred during the study, regardless of the manipulations and procedures received by the volunteer, should be reported to the NMRC TPID within one working day after the serious AE occurred.

The completed Suspicious Adverse Reaction Reporting Form (Appendix 5) should be sent by confidential mail to the following address of the Ministry of Health of Russia: [name].

If important additional information is discovered after the initial report, subsequent reports should be sent (using the same form).

#### **11.4 Expedited reporting of suspected unexpected serious adverse events by the Principal Investigator to the LEC**

Deadlines for notifying the LEC of a suspected unexpected serious adverse reaction (SUSAR) after the initial information about the SUSAR was received:

- For a SUSAR that resulted in death or a life-threatening condition, a notification should be submitted within seven (7) calendar days after the SUSAR became known to the NMRC TPID; the report should be submitted in additional eight (8) calendar days
- For other SUSARs that are reported within fifteen (15) calendar days after the SUSAR became known to the LEC (prior notification is not required)

The Safety Report Form for reporting a suspected adverse reaction must be used in SUSAR reports.

## 12. DATA MANAGEMENT AND STATISTICAL ANALYSIS

### 12.1. General provisions

Data on the proportion of subjects who tested negative in a population of healthy subjects who are not at risk of tuberculosis are of key importance in the development of the RTA test.

The obtained results will allow us to conclude about the significance of the RTA test in the detection of tuberculosis infection.

The NMRC TPID shall be responsible for the management of the clinical study and statistical analysis of data received from all study sites.

### 12.2 Data management

Clinical data are collected in the CRF. The original CRFs remain in the custody of the study site. The NMRC TPID will receive copies of CRFs completed at each visit from the Responsible Investigators.

The Investigator shall be responsible for proper documentation of data in the CRF of each subject and related records. The Investigator signing the protocol signature page shall personally sign the CRF to ensure that observations and findings are correctly and completely documented in the CRF. Copies of CRFs should be submitted to the NMRC TPID on time and will be kept by the Principal Investigator in a designated storage area. Investigators will be requested to clarify any ambiguous or implausible data if any.

### 12.3 Analyzed populations

The population for the safety analysis includes all participants who had one RTA test during the study.

The efficacy population will be equivalent to the per-protocol population and will comprise all participants who have met the inclusion criteria.

### 12.4 Statistical methods

The study involves the analysis of anonymized CRF data that will be performed using an MS Excel spreadsheet:

- Study subject number;
- Enrollment date;
- Sex;
- Date of birth;
- BCG vaccination status (presence of a scar);
- Height;
- Body weight;
- Complaints;
- Body temperature;
- RR per minute;
- HR;
- BP (mmHg);

- Lung auscultation: rhonchi or crackles;
- The RTA test result (mm);
- The T-SPOT.TB assay result.

Generally accepted statistical methods will be employed to analyze the study data using Microsoft® Excel® 2016 MSO application software package (version 2109 16.0.14430.20154, 32-bit, product code: 00333-59091-97459-AA884). The use of the software is planned for statistical analysis. Two-sided statistical tests at a statistical significance level of  $p < 0.05$  will be used.

Demographic and other baseline characteristics will be presented for all patients enrolled in the study (the full analysis set population).

The Shapiro-Wilk criterion will be used to determine the normality of the distribution. Parameters that are quantitative variables (including age) will be expressed as:

- Arithmetic mean (mean);
- 95% CI for the mean;

Qualitative and categorical variables (gender, etc.) will be expressed in absolute values (n/N) and proportions (%).

The study will evaluate the specificity of the RTA test (see. Paragraph 9.3.1).

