The following normative documentation regulates the use of the RTA test in Russia: Order of the Ministry of Health of the Russian Federation No. 855 of October 29, 2009; Order of the Ministry of Health of the Russian Federation No. 951 of December 29, 2014; Order of the Ministry of Health of the Russian Federation No. 124H of March 21, 2017; the clinical guidelines “Latent tuberculosis infection in children,” “Tuberculosis in children” (Moscow, 2020) [10], and the clinical guidelines “Tuberculosis in adults” (Moscow, 2020) [11].

RTA has been used in the Russian Federation and CIS since 2009. More than 60 million tests have been performed since its authorization. In 2015, per Order of the Ministry of Health of Russia No. 951 of December 29, 2014, the RTA test replaced the Mantoux test in the screening of tuberculosis in children 8 years of age or older.

Studies have shown a significant increase in tuberculosis rates (37-fold in schoolchildren aged 8–17 years compared with the Mantoux test [12]) in primary healthcare centers following the transition to the screening using RTA.

The specificity of the RTA test was also evaluated in a local (Moscow) patient population with a low tuberculosis rate and a low risk of tuberculosis infection (contacts of pregnant women). In 2015–2016, 7,249 tests were performed in this population which most closely mirrors the permanent population of Moscow. A positive or equivocal RTA test result was found in 0.3%

(95% confidence interval [CI] 0.2–0.6%) and 1.0% (95% CI 0.7–1.4%) of evaluated pregnant contacts ( $p < 0.05$ ) in 2015 and 2016, respectively. No tuberculosis patients were identified in this population. Thus, the specificity of the test was 99.0–99.7% [13].

With decreasing incidence of tuberculosis in the Russian Federation, it seems relevant to confirm the specificity of the RTA test in a population of healthy subjects who are not at risk of tuberculosis (with a negative T-SPOT.TB assay result) in real clinical practice in the subjects of the Russian Federation with low rates of tuberculosis incidence and mortality.

It should be noted that specificity, which is one of the key characteristics of a diagnostic test, is defined as the ability of a test to correctly identify subjects without the disease.

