### 7.3 Primary endpoint

- Absolute number and percentage of the volunteers with negative and positive test results with RTA (individuals with no signs of tuberculosis infection) based on the results of the assessment (measurement) of the infiltrate 72 hours after the test.

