### 7.5 Primary variables:

Diameter of the infiltrate (papule) at the injection site, measured across the longitudinal axis of the forearm 72 hours after the intradermal test.

[figure not shown]

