### 9.2 Procedure

The RTA intradermal test is performed according to the current prescribing information for the medicinal product. An RTA dose of 0.1 mL is injected into the inner surface on the mid-third of the right or left forearm. The injection is performed using a 1-mL syringe with a short beveled needle (a tuberculin syringe).

A qualified healthcare professional will read the result of the skin test (diameter of hyperemia/infiltrate (papule) in mm) 72 hours after the RTA injection. An infiltrate (papule) of any size will be considered a positive result.

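### Section 12.4 offers only a mean and 95% CI for quantitative variables; applied to infiltrate diameter at the specificity cited in Section 6, the interval would usually be (0, 0) or extend below zero

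*Combined protocol and SAP*

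**What the plan says.** Section 7.5 defines the primary variable as "Diameter of the infiltrate (papule) at the injection site, measured across the longitudinal axis of the forearm 72 hours after the intradermal test". Section 12.4 lists the fields of the analysis file, one of which is "The RTA test result (mm". It then gives a single rule for numerical data, "Parameters that are quantitative variables (including age) will be expressed as", followed by two items: the arithmetic mean and the "95% CI for the mean". No SD, median, range or other summary is listed.

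Just before that rule, Section 12.4 states: "The Shapiro-Wilk criterion will be used to determine the normality of the distribution". It does not say what changes if normality is rejected.

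Two other sections bear on the point. Section 9.2 sets the reading rule: "An infiltrate (papule) of any size will be considered a positive result". A negative result is therefore a diameter of 0 mm. Section 7.3 defines the primary endpoint as "Absolute number and percentage of the volunteers with negative and positive test results with RTA", and Section 9.3.1 defines specificity as a proportion.

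**The concern.** A mean with a normal-theory interval suits roughly symmetric measurements. Infiltrate diameter in this cohort is not of that kind. Volunteers are healthy and T-SPOT.TB negative, so most diameters should be exactly zero, with a few positive values. When non-zero values are very few, the interval either collapses to a single point or extends to impossible negative diameters, and it no longer covers the true mean 95% of the time.

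The normality test looks like a safeguard but is not one. It would reject for such data, yet the plan attaches no consequence to rejection, so the same mean and interval would be reported.

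At stake is a misleading line in the report for a variable labelled primary. A mean over all volunteers also mixes how often reactions occur with how large they are, and so says little about the size of the false-positive reactions.

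**Working it through.** **Inputs from the documents.** N = 150 (Section 8.3). A negative result is 0 mm (Section 9.2). Specificity is 99.0–99.7% in Section 6, where positive and equivocal results were counted together, and 0.9 in Section 12.5.

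**Assumptions not in the documents.** The interval is a t-interval, since the plan names no method. All 150 volunteers are evaluable. Non-zero diameters are uniform on 3–15 mm in the main calculation; other shapes were tried as well.

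**The plan's own figures.** Section 12.5 uses SD = √(u(1−u)/N). At u = 0.5, √(0.25/150) = 0.041. At u = 0.9, √(0.09/150) = 0.0245, which the plan gives as 0.024. Both reproduce. They concern the proportion, not the diameter.

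**When the interval degenerates.** Suppose k of 150 volunteers have papules of equal diameter d and the rest have 0. Then

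- mean = kd/150
- SE = d·√[k(150−k)/(150²·149)]
- mean/SE = √[149k/(150−k)], in which d cancels.

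The lower limit is below zero when this ratio is less than t(0.975, 149) = 1.976.

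| k | mean/SE | lower limit if d = 8 mm |
|---|---|---|
| 0 | – | interval is (0, 0) |
| 1 | 1.00 | −0.05 mm |
| 2 | 1.42 | −0.04 mm |
| 3 | 1.74 | −0.02 mm |
| 4 | 2.02 | just above 0 |

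With equal diameters, up to three positives give a degenerate or negative interval. Unequal diameters extend this to larger k.

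**How often that happens.** With k binomial(150, 1 − specificity):

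- Specificity 0.997: 150 × 0.003 = 0.45 positives expected; P(k = 0) = 0.997^150 = 63.7%; P(k ≤ 3) = 99.9%.
- Specificity 0.990: 1.5 expected; P(k = 0) = 0.99^150 = 22.1%; P(k ≤ 3) = 93.5%.
- Specificity 0.9: 15 expected; P(k = 0) is negligible; P(k ≤ 3) = 0.012%.

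**Coverage (40,000 simulated trials per setting).** A (0, 0) interval always misses a positive true mean, so coverage cannot exceed 1 − P(k = 0). That ceiling is 36.3% at 0.997 and 77.9% at 0.990, whatever the papule sizes.

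| Specificity | (0, 0) or negative lower limit, uniform 3–15 mm | Coverage, uniform 3–15 mm | Coverage, other shapes |
|---|---|---|---|
| 0.997 | about 99.9% | about 37% (at the 36.3% ceiling, within simulation error) | about 36% |
| 0.990 | about 97% | about 73% | 71–78% |
| 0.9 | under 0.3% | about 93% | 92–93% |

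The other shapes were constant 8 mm, uniform 2–15 mm and lognormal with median 7 mm. Across them, the share of degenerate or negative intervals was 94–98% at 0.990, 65–84% at 0.98, 34–59% at 0.97, 5–17% at 0.95 and 0.01–0.24% at 0.9. The problem becomes the usual outcome only above roughly 97–98% specificity.

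**The case against.** The best defence is that the mean and CI rule is a convention for the baseline table. It directly follows the sentence on demographic and baseline characteristics, age is its only named example, and specificity has its own closing sentence in Section 12.4. Section 9.2 also has hyperemia or infiltrate read in mm, so the field in mm may not be infiltrate alone. It is true that diameter is covered by inference rather than by name. But the rule is worded for quantitative variables without exception, diameter is one, and no other summary in mm is given. An analyst following the text would apply it.

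Second, Section 12.5 plans on 0.9, and the Section 6 figure comes from a different group (contacts of pregnant women in Moscow). This stands as a limit on size: at 0.9 the interval behaves tolerably. However, Section 12.5 calls 0.9 more realistic in contrast to the worst case of 0.5, and adds that earlier studies exceeded 90%. The higher range therefore cannot be set aside.

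Third, a reader might infer that the mean is the only planned summary of the RTA reading, or that the specificity result is compromised. The documents do not support this. Sections 7.3 and 9.3.1 already turn the measurement into a count, a percentage and a proportion, and no conclusion or sample-size figure rests on mean diameter.

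Fourth, a CI for the mean of age or weight is less informative than a spread, but with 150 volunteers it is not invalid. Asking for an SD there is mainly a matter of reporting convention. Individual diameters remain in the analysis file, so nothing prevents listing the positives; the plan simply does not call for it.

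**Conclusion.** The point holds as a conditional one about a descriptive summary. By its general wording Section 12.4 applies a mean and 95% CI to infiltrate diameter, and its normality test has no consequence; the latter is true at any specificity. The failure of the interval depends on specificity. It is near certain, with coverage well below nominal, across the 99.0–99.7% range in Section 6, and nearly absent at 0.9. The coverage figures rest on a t-interval, 150 evaluable volunteers and assumed papule sizes. The chance of a (0, 0) interval and the resulting coverage ceiling do not depend on papule sizes.

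It would go too far to say that the interval will fail whatever the true specificity, or that the primary result is at risk. The change is worth making because the rule serves this variable poorly and replacing it costs almost nothing.

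**What to change.** In Section 12.4:

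- Exclude infiltrate diameter from the mean and 95% CI rule, and state that the RTA field in mm means infiltrate diameter as in Section 7.5.
- Keep n/N (%) positive as the primary summary, as Section 7.3 already has it.
- For positive volunteers only, report the median, minimum–maximum and a by-volunteer listing of diameter in mm.
- Either drop the Shapiro-Wilk test or tie it to a stated alternative, such as median and range when normality is rejected.
- Optionally, add SD and range for age, height, weight and vital signs.

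The cost is a few lines of wording. No extra data, visits or volunteers are needed, and the sample size is unchanged.
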